## 3. STUDY DESIGN

Diagnostic prospective cohort study: mass screening through conventional symptoms screening by a doctor, a physical exam and with testing of CAD4TB® and AeoNose™ as well as bacteriological testing of presumptive cases.

An estimated 5000 individuals will be invited to participate. All prisoners and employees will be eligible for inclusion. The sample size is based on an estimated incidence of 3000-5000/100.000 and a presumptive number of 150-250 active TB cases to be found in order to have enough cases to first train the neural network (with at least 500 - 1000 healthy individuals and a 100 active TB cases) and then perform the blind predictions on the rest of the participants to establish sensitivity and specificity of the AeoNose™.

The study consists of one primary visit and, in case of suspicion of presumptive TB but no confirmed TB or alternative diagnosis, two follow-up visits after three and six months respectively. The estimated total study duration will be from February 2020 to May 2021. The study settingwill be the Buen Pastor, Esperanza and Tacumbú prisons in Asunción, Paraguay Required condition to perform the study in each of these three institutions is safety for the study team and also the guards and prisoners. In case of unstable conditions we will look for an alternative penal institution.

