The digital CXR image will be analysed by CAD4TB® and the doctor will interprete the CAD4TB® output score and check the CXR for alternative diagnosis. All the findings by the study doctor will be recorded in the digital case record form. At the end of this visit the doctor will decide on health status of the participant: either the participant is considered healthy or a presumptive TB case.

For healthy participants the study ends after this 5th station.

- 6. Presumptive TB cases (see 6.1.1 Case definitions) will be asked to produce two sputum samples outside, preferably in the open air. Sputum can be either be produced spontaneously or via sputum induction with nebulized saline. Saline solution will be nebulized using a portable nebulizer. Sputum samples can deposited in standard containers. Samples will be stored in a cool box and transported to the laboratory the same day. Samples will then be processed and analysed by the National Reference Laboratory, Laboratory San Alfonso and IICS using GeneXpert® molecular testing and MGIT mycobacterial culture.
- 7. All participants will be educated about the importance of seeking medical care if symptoms compatible with TB emerge at any time.
- 8. In case a participant is passively identified with TB during the study period by the prison health services or PNCT, the study researchers will be notified. Clinical and microbiological data will be shared based on informed consent given by the participant.

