#### Follow-up of presumptive TB cases

Participants who are considered presumptive cases of TB at Visit 1, but with negative sputum results or unable to produce sputum, will be followed-up after three and six months.

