## TB case:

A participant in whom TB has been confirmed bacteriologically, or a participant who started treatment empirically and showed response to treatment after the initial phase of TB treatment, as documented by the PNCT.

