## 8. STATISTICAL ANALYSIS

All data will be analysed using SPSS software. (IBM, United States) The data of the participants will be analysed cross-sectional. Follow-up of participants with presumptive TB but negative microbiological testing will be completed until 6 months after Visit 1. After a

follow up period of 6 months a final diagnosis will be made (either healthy or TB case and the participant will be offered treatment if indicated). A p-value (two-sided) < 0.05 is considered to indicate a statistically significant difference in all comparisons. Multivariate analysis will be performed to analyse influences of different combinations of participant characteristics.

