#### 8.1 Primary study parameter(s)

Primary study parameters are the number of TB cases cases by CAD4TB® CXR analysis and AeoNose™ breath sampling.

A binary assessment of the presence or absence of illness has four possible outcomes: true positives (TP), false positives (FP), true negatives (TN) and false negatives (FN). The relationship of the four outcomes is the basis of sensitivity and specificity analysis which determines the accuracy and predictive value of a diagnostic tool.

*True positive:* A positive test result in a confirmed TB case.

*False positive*: A positive test result with negative sputum results and no confirmed TB during follow-up.

*True negative*: A negative test result with no confirmed TB during follow-up. *False negative*: A negative test result with confirmed TB during follow-up.

Receiver operating characteristics (ROC) will be generated using an ROC package, and bootstrapping to generate confidence intervals in the ROC plot. T-testing or McNemar's test will be used to compute P values when comparing the sensitivity of conventional screening and CAD4TB® and AeoNose™ at assumed levels of specificity. We will also use multivariate analysis to analyse influences of different combinations of participant characteristics.

CAD4TB®: The collection of digital CXR images will be analysed and compared to presumptive and confirmed cases. The number of true/false positives and negatives will be used to calculate sensitivity and specificity as described above. The predictive value of the test will be analysed.

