#### 10.4 Temporary halt and (prematurely) end of study report

The investigator/sponsor will notify the accredited MREC of the end of the study within a period of 8 weeks. The end of the study is defined as the last patient's last visit. The sponsor will notify the MREC immediately of a temporary halt of the study, including the reason of such an action.

In case the study is ended prematurely, the sponsor will notify the accredited MREC within 15 days, including the reasons for the premature termination.

Within one year after the end of the study, the investigator/sponsor will submit a final study report with the results of the study, including any publications/abstracts of the study, to the accredited MREC.

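### Passively notified TB is collected over a calendar period with no limit counted from each participant's Visit 1, and the protocol conflicts on whether such cases count in people judged healthy

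*Protocol*

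**What the plan says.** Section 3, Visit 1, step 8 sets the passive route: "In case a participant is passively identified with TB during the study period by the prison health services or PNCT, the study researchers will be" informed of it, and clinical and microbiological data are then shared with the study under the participant's consent. The study period is calendar time. Section 3 gives it as "The estimated total study duration will be from February 2020 to May 2021", and section 10.4 closes it for everyone at once: "The end of the study is defined as the last patient's last visit".

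The only time limit counted from a participant's own Visit 1 concerns presumptive participants. Those with negative sputum, or unable to produce sputum, "will be followed-up after three and six months". Section 8 repeats the limit: "Follow-up of participants with presumptive TB but negative microbiological testing will be completed until 6 months after Visit 1".

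For everyone else, section 3 says: "For healthy participants the study ends after this 5 th station". Section 8 also describes the analysis as cross-sectional.

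The outcome definitions carry no time limit. In section 6.1.1 a TB case begins with "A participant in whom TB has been confirmed bacteriologically". In section 8.1 a false negative is "A negative test result with confirmed TB during follow-up", and a true negative is the mirror image. Neither says what follow-up means for a participant who has no scheduled follow-up.

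**The concern.** Reference status in this study is partly a matter of how long a person is observed. Participants judged healthy are not sampled at Visit 1 and are not seen again, so step 8 alone can move them from true negative to false negative. If step 8 feeds the accuracy cells, two people with the same results and the same later course can land in different cells because one was enrolled in February and the other in November.

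The first main endpoint (total TB cases) and the sensitivity of both devices would then depend partly on the enrolment calendar. The devices would also be affected unequally. Under section 6.1.1 a CAD4TB score above the referral threshold makes a participant presumptive. Anyone correctly classed as healthy was therefore CAD4TB-negative at that threshold, and a later counted case is necessarily a CAD4TB miss there. AeoNose plays no part in referral and could be positive or negative. Section 8.1 plans to compare sensitivities. It also draws the AeoNose calibration set from the whole study period to avoid bias over time and between institutions, an aim that enrolment-dependent case labels would work against.

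**Working it through.** **1. The plan's own figure.** Section 3 expects 150-250 cases among 5000 people at 3000-5000 per 100,000: 5000 × 0.03 = 150 and 5000 × 0.05 = 250. It reproduces, and it shows that the rate is used as the yield of the screening round.

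**2. People affected.** The summary expects 20-30% to be presumptive, so 70-80% are judged healthy: 5000 × 0.70 = 3500 to 5000 × 0.80 = 4000 if everyone invited takes part. At the 72% average consent cited in section 4.3, this is 3600 × 0.70 = 2520 to 3600 × 0.80 = 2880.

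**3. Length of the passive window.** Window = study end minus Visit 1 date.
- First enrolees, February 2020 to May 2021: 14.0 to 15.9 months depending on the days within each month, so about 15.
- Last enrolees: 6 months if the last Visit 1 falls about November 2020, so that a six-month visit fits by May 2021.
- Ratio 15/6 = 2.5. Mean under even enrolment (15 + 6)/2 = 10.5 months.

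The lower end is inferred, because the protocol gives no enrolment end date. A last enrolee who is judged healthy, or confirmed at Visit 1, needs no later visit, so the shortest window could be under 6 months. Faster enrolment would narrow the spread.

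**4. The two readings.**
- Counted: step 8 (calendar period), section 6.1.1 (no time limit) and section 8.1 (follow-up undefined for healthy participants) make a passive case reference-positive whenever it arises before study end.
- Not counted: the study ends at station 5 for healthy participants, the analysis is cross-sectional, and follow-up as a study activity is described only for presumptive cases.

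The text does not choose between them.

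**5. A hypothetical illustration.** None of these inputs is in the protocol: 200 baseline cases of which 180 are detected (90%), 3750 people judged healthy, a yearly rate r of later notified TB, and 20% of those cases test-positive at Visit 1.

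Late cases L = 3750 × (1 − exp(−r × months/12)). Apparent sensitivity = (180 + 0.2L)/(200 + L).

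| r per year | all watched 6 months | mean 10.5 months | all watched 15 months |
|---|---|---|---|
| 0.5% | L = 9.4, 86.9% | L = 16.4, 84.7% | L = 23.4, 82.7% |
| 1% | L = 18.7, 84.0% | L = 32.7, 80.2% | L = 46.6, 76.8% |
| 3% | L = 55.8, 74.7% | L = 97.2, 67.1% | L = 138.0, 61.4% |

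At 1% per year, counting any passive cases within 6 months costs 90.0 − 84.0 = 6.0 points. The open-ended window costs a further 84.0 − 80.2 = 3.8. If a device detects none of the late cases, as CAD4TB would at the referral threshold, the 10.5-month figure is 180/232.7 = 77.4% rather than 80.2%.

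**The case against.** The strongest reply is that the central consequence is never stated. Step 8 says that researchers are told and data are shared. It does not say that a notification in someone judged healthy enters the accuracy cells. The statements listed under the second reading suggest that follow-up in section 8.1 means the three- and six-month visits, in which case no false negative depends on calendar date. **This stands.** A reader might infer that a person judged healthy in February 2020 and diagnosed 14 months later is, under the protocol, a false negative. The text allows that reading but does not impose it. It does not exclude it either, since sections 6.1.1 and 8.1 set no limit and step 8 collects exactly these cases.

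A reader might also put a firm size on the effect by applying 3-5% as a yearly rate to 3500-4000 healthy participants, with 25-50% notified. Cases beyond six months would be 3500 × 0.03 × 4.5/12 × 0.25 = 9.8 to 4000 × 0.05 × 4.5/12 × 0.50 = 37.5. A sensitivity of 190/200 = 95% would then fall to 190/209.8 = 90.5% or 190/237.5 = 80.0%. **The documents do not support this.** It applies the screening yield again, as new disease, to people who have just been screened. It assumes full consent, and the notified share has no source. It also holds baseline cases at 200 when 5% implies 250; with 250 the lower figure is 237.5/287.5 = 82.6%.

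On those same inputs a six-month window would still admit 13 to 50 passive cases (52.5 × 0.25 to 100 × 0.50), leaving 190/213.1 = 89% to 190/250 = 76%. Much of the apparent loss therefore comes from counting later disease as missed at all, not from unequal windows.

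Two further limits stand. The CAD4TB asymmetry holds at the referral threshold, which is still to be determined, and section 8.1 also plans ROC analysis at other cut-offs. The protocol specifies no between-prison comparison, so harm to one would concern an unplanned analysis.

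The handling could be settled in a statistical analysis plan that is not shown. But the protocol itself sets the collection window and defines the four cells, and those statements conflict as written.

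**Conclusion.** The point holds in a conditional form. Step 8 collects passive TB over calendar time, no limit runs from Visit 1 for participants judged healthy, and the protocol conflicts on whether these cases count. If they count, the period at risk of becoming a false negative runs from about 15 months for the first enrolees to about 6 or fewer for the last, assuming enrolment until about November 2020. At the referral threshold such cases would all be CAD4TB misses, while AeoNose could go either way. If they do not count, the inequality disappears, but the protocol should say so.

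The effect on sensitivity cannot be computed from the protocol, and every sensitivity figure above is hypothetical. The case for correction rests on the conflicting text and the unequal window, not on a projected loss.

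**What to change.** In step 8 and section 8.1, state that passively notified TB counts in the first main endpoint and in the true/false positive/negative cells only if diagnosed within one fixed window from that participant's Visit 1. The six months already used in section 8 is the natural example. Add a sensitivity analysis with a shorter window, such as three months, because disease arising after screening can still be counted as missed within six.

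Record the diagnosis date; step 8 mentions clinical and microbiological data but not the date. Keep notification open until the window has closed for the last enrolee, including one judged healthy. List later notifications separately, outside the accuracy cells. Reconcile step 8 with the statement that the study ends at station 5, for example by saying that visits end there while notification continues for the fixed window.

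The cost is a sentence or two in each section and one date field, with no extra visits or tests. The downside is that a few slow cases truly missed at Visit 1 but diagnosed after the window leave the sensitivity denominator.

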#### Follow-up of presumptive TB cases

Participants who are considered presumptive cases of TB at Visit 1, but with negative sputum results or unable to produce sputum, will be followed-up after three and six months.

#### Visit 2 and 3 (at three and six months after Visit 1)

Study procedures are the same as Visit 1 steps 1 through 5. Participants will be asked for symptoms, have a physical exam, undergo CXR with CAD4TB® and AeoNose™ breath sampling. At visit 2 and 3, all participants will be asked to produce two sputum samples. In case of positive results for *Mycobacterium tuberculosis*, confirmed cases will be notified to

the PNCT. After visits 2 and 3 a decision will be made by the study team on the final health status of the participant (either considered healthy or a TB case). In case of a high suspicion of TB the prison health authorities and the PNCT may decide to treat this individual for active TB. The result of this anti-tuberculosis treatment will be communicated with the study team.

#### Referral of TB cases and non-TB illness

In case of a positive culture result or GeneXpert® with *Mycobacterium tuberculosis*, the participant will be informed and the PNCT will be notified through the prison authorities. GeneXpert® will provide a test result within 24 hours.

In compliance with the current Paraguayan national TB treatment guidelines, established TB cases will start anti-tuberculous therapy and will be followed-up by the PNCT and prison health service.

For presumptive TB case with signs of severe illness but a negative GeneXpert® result, the PNCT and the prison health service will be notified. The prison health service and PNCT may decide whether it is justified to start empiric treatment for TB. This decision will be made available to the investigators who will review these cases afterwards to categorize them according to the formal case definitions.

If a participant presents to the study doctors with signs and symptoms compatible with severe illness, the prison health service will directly be notified in order to take an appropriate action.

If the digital CXR shows pathological abnormalities not being consistent with tuberculosis, the participant will be informed and referred to the prison health service.

## 4. STUDY POPULATION

## 4.1 Population (base)

Persons deprived of liberty (PPL) adults (≥18 years) and personnel of the three penitentiary centers of Paraguay (Buen Pastor, Esperanza and Tacumbú prison) in Asunción. Both male and female (estimated 90% vs. 10%). Ethnicity is mostly mixed / Latin-American as well as indigenous from several different ethnicities.

#### 4.2 Inclusion criteria

 All persons, either being a prisoner or employee, of the involved penal institutions after providing informed consent, including those with known active TB disease and/or currently on TB treatment.

#### 1. Exclusion criteria

A potential participant who meets any of the following criteria will be excluded from participation in this study:

- 1. Unable to exhale breath through the AeoNose™ during five minutes due to respiratory insufficiency
- 2. Unable to stand in an upright position for the CXR
- 3. Unable to communicate and comply with the instructions of the study team

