#### 2. OBJECTIVES

Primary Objective:

- Assessment of the sensitivity and specificity of the AeoNose™ and its utility for mass TB screening.
- 2. Evaluation of the feasibility and utility of CAD4TB® digital CXR as mass screening tool for TB in high incidence settings.
- 3. Identification of factors that affect diagnostic accuracy of AeoNose™ and CAD4TB®.

Secondary Objective(s):

- 1. Assessment of TB epidemiology in Paraguayan prisons and identification of mycobacterial strains.
- 2. Assessment of cost-effectiveness and cost-efficiency of mass screening programs integrating digital CXR with CAD4TB®, AeoNose™ or both techniques in conjunction.
- 3. Characterization of transmission dynamics and potential measures for transmission reduction.

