#### 4.3 Sample size calculation

Based on WHO definitions, mass screening includes every person in a vulnerable community. The combined prisons of Tacumbú, Esperanza, Buen Pastor house around 4700 PPL. An additional 500 employees (estimated number, to be confirmed) who are in direct contact with the PPL will also be included. Based on calculations we expect to detect around 200-240 cases of active tuberculosis in prisoners (3-6% of 4000 PPL) and 0-5 cases in employees (estimated 0.2% of 1000 employees). The number of expected cases in the latter group could be an underestimation as these people are in constant contact with PPL and have a higher risk than the general population of active TB.

The study sample size is based on the need for at least 100 cases with active TB to build a robust AeoNose™ neural network (calibration model) and subsequently another 100-150 cases to make a blind prediction (validation model). A systematic literature review of acceptability of TB screening among risk groups showed an average percentage of screening consent of 72% among prisoners. (range 18-100%, Mitchell et al. 2012)

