#### 9.3 Benefits and risks assessment, group relatedness

Prior to this study, none of the prisons perform the entry and/or annual TB screening recommended by WHO and ECDC (WHO, Geneva 2013; ECDC Stockholm/Lisbon 2018). TB cases are currently detected actively by trained prison health promotors and passively by seeking medical consultation due to symptoms. As TB often manifests with a prolonged period of mild or unspecific symptoms, many patients remain undiagnosed, untreated and contagious for a long period. Participation in the screening offers the participant an opportunity to be checked for TB. The mass screening offered in this study is an opportunity for the PNCT to comply with WHO recommendations for prison screening and thus improving the prisoners' healthcare and reducing the continuous spread of TB within and from the prisons. After this study the PNCT will possess accurate information on the prevalence of TB within Paraguayan prisons which can serve as the basis for future policy and program enhancements. CAD4TB® analysis brings no burden to the participant. Breath sampling with the AeoNose™ device is risk-free and a minimal burden for the participant. Group-relatedness is inherent in a mass screening study of a known high risk population. For an accurate assessment of the prevalence of TB in the prisons and the utility of the CAD4TB® and AeoNose™ as a screening tool the entire group needs to be investigated without any inadvertent selection of participants.

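### A person who cannot do one index test is excluded from the whole study, against the protocol's own entire-group aim; TB prevalence may be understated and people AeoNose cannot test go uncounted

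*Protocol*

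**What the plan says.** The Exclusion criteria (directly after Section 4.2) state that anyone meeting any one of three criteria "will be excluded from participation in this study". Criterion 1 is inability to breathe out through the AeoNose "during five minutes due to respiratory insufficiency". Criterion 2 is "Unable to stand in an upright position for the CXR". Criterion 3 concerns communication and compliance and is not at issue.

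Other sections describe complete coverage:

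- Section 3: "All prisoners and employees will be eligible for inclusion", and "An estimated 5000 individuals will be invited to participate".
- Section 4.3: "mass screening includes every person in a vulnerable community".
- Section 9.3, on what accurate prevalence and the utility of both tools require: "the entire group needs to be investigated without any inadvertent selection of participants".

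The first main endpoint (Section 6.1.2) is the total number of TB cases found. Section 2 makes the utility of AeoNose for mass screening part of the first primary objective and lists "Assessment of TB epidemiology in Paraguayan prisons" as a secondary objective.

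**The concern.** Criterion 1 is a limit of one device and criterion 2 a limit of one imaging procedure, but either ends participation altogether. Someone too breathless for the AeoNose may still be able to give a symptom history, have a chest X-ray scored by CAD4TB and provide sputum. Someone who cannot stand may still manage tidal breathing through a portable device. As written, none of that information enters the study.

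The selection is unlikely to be neutral. Criterion 1 is tied to respiratory insufficiency in a study of a mainly pulmonary disease, and the protocol treats dyspnoea both as a sign of TB (Section 3, Visit 1) and as a component of the clinical severity score (Section 6.1.1). If the excluded have more TB than the rest, the case count and prevalence are too low and the severe end of the spectrum is thinned.

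For AeoNose there is a further issue. How often a device cannot be used is part of its utility for mass screening. If those people are never in the study, that share does not appear. An analysis plan could not repair this, because data that were not collected cannot be recovered.

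**Working it through.** **The plan's own figure.** Section 3 expects 150-250 active cases among 5000 people at 3-5%. 5000 × 0.03 = 150 and 5000 × 0.05 = 250, so the figure reproduces.

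**Inputs**

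- From the protocol: N = 5000; true prevalence π = 3% or 5% (Section 3); illustrative AeoNose sensitivity 88% (Section 5.2, Paraguayan pilot); illustrative CAD4TB sensitivity 95% (Section 1).
- Assumed, because the documents give neither: share excluded e = 0.2-2% (10-100 people); TB prevalence among the excluded p = 10-40%.

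**Prevalence**

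Cases lost = N·e·p. Observed prevalence = (N·π − N·e·p) / (N − N·e).

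| Assumption | Cases lost | True 3% observed as | True 5% observed as |
|---|---|---|---|
| e = 0.2%, p = 10% | 10 × 0.10 = 1 | 149/4990 = 2.99% (−0.5%) | 249/4990 = 4.99% (−0.2%) |
| e = 1%, p = 20% | 50 × 0.20 = 10 | 140/4950 = 2.83% (−5.7%) | 240/4950 = 4.85% (−3.0%) |
| e = 2%, p = 40% | 100 × 0.40 = 40 | 110/4900 = 2.24% (−25.2%) | 210/4900 = 4.29% (−14.3%) |

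Brackets show relative bias. It is downward whenever p exceeds π and zero when they are equal. Numerator and denominator both scale with N, so the relative bias does not depend on the number screened.

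**CAD4TB sensitivity**

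Let f be the share of all cases that is lost, and suppose every lost case would have scored positive. Sensitivity in all cases = 0.95(1 − f) + f.

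- Middle row: f = 10/150 = 6.7% gives 95.3%; f = 10/250 = 4% gives 95.2%.
- Extreme: f = 40/150 = 26.7% gives 96.3%.

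The shift is about one point at most. A shift the other way would need the excluded, plausibly sicker, cases to score worse than the rest.

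**AeoNose sensitivity**

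- Lost cases counted as missed, 0.88(1 − f): 82.1% (π = 3%) or 84.5% (π = 5%) in the middle row, and 64.5% at the extreme.
- Lost cases counted as would-be positives, 0.88(1 − f) + f: 88.8% or 88.5% in the middle row, and 91.2% at the extreme.

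The direction therefore depends on how an untestable case is counted. The first set charges every excluded case to AeoNose, including people excluded only because they cannot stand, so it is a worst case and not an estimate.

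**The case against.** **The group may be very small.** Only tidal breathing is needed, and Section 6.2 lets an interrupted sample, for example after coughing, be restarted. Only failure caused by respiratory insufficiency excludes. This stands, and it is why the range starts at one lost case. It does not help those who meet the criterion.

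**Refusal matters more.** At the 72% average consent quoted in Section 4.3, 28% of 5000, or 1400 people, would not take part, far more than 10-100. True, but refusal is not under the protocol's control and is not defined by respiratory illness; this exclusion is both.

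**Section 9.3 bars only inadvertent selection.** Stated feasibility criteria are deliberate, so a reader who infers a literal ban on any selection goes too far. The conflict is with the requirement that the entire group be investigated, and with the matching statements in Sections 3 and 4.3.

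**Paired comparisons need both tests.** Section 8.1 foresees McNemar's test, which uses people with both results. That justifies restricting the paired analysis, not the study population.

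**Severely ill people are referred.** Section 3 has the prison health service notified of severe illness. That concerns care and does not restore anyone to the case count.

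**Data already collected may be kept.** The X-ray is the third station and breath sampling the fourth. The protocol does not say when eligibility is checked, or that an X-ray is discarded if breath sampling then fails. A reader might infer that CAD4TB results are thrown away; the text leaves this open. Nor does it forbid counting and reporting exclusions.

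**Conclusion.** The point holds as an inconsistency with a plausible but unquantified consequence. The whole-study scope of criteria 1 and 2 contradicts Sections 3, 4.3 and 9.3. It may understate the case count and prevalence, thin the severe end of the spectrum, and leave people AeoNose cannot test out of its assessed utility.

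The size rests wholly on the two assumed inputs. The middle case, a relative prevalence bias of -3% to -6%, is modest; the -25% end needs 2% excluded, 40% of them with TB, and a true prevalence of 3%.

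Two stronger readings are tempting and not supported. One is that both tests' accuracy is biased: CAD4TB sensitivity moves by about one point at most under the assumptions shown, and the direction for AeoNose is not fixed. Specificity was not modelled; little change is expected, since at most 2% of people, mostly without TB, are removed. The other is a specific figure for AeoNose sensitivity in all cases, with the excluded counted as missed. That would charge AeoNose with people who merely cannot stand. It would also ignore that AeoNose accuracy comes only from cases left after calibration, which takes at least 100 cases by Section 4.3 or at least 30-40% of them by Section 8.1.

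The change is worth making because it is cheap and the loss cannot be repaired at analysis.

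**What to change.** Reconcile the Exclusion criteria with Sections 3, 4.3 and 9.3:

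1. Make criteria 1 and 2 test-specific. A person who meets one of them stays in the study, in the TB case count and in the analysis of the test they can do. Keep whole-study exclusion for criterion 3 only.
2. Record *no valid AeoNose result* and *no CXR* as separate outcomes, and report the numbers by test.
3. Add a sensitivity analysis in which an AeoNose no-result in a TB case counts as not detected.
4. Restrict paired comparisons to people with results on both tests.

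Suitability for sputum induction and other clinical handling of these people should be left to the study's clinicians. Since the risk and insurance statements in Sections 7.2.4, 9.4 and 11 were written for a population without them, those sections should be reread when the amendment is made.

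The cost is amendment wording and a few participants with incomplete index tests, who drop out of the paired comparisons. No new procedure is introduced.
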